After randomization to RVX000222 or placebo, visits will occur every 2 weeks until Week 12. From Week 12 to 28, visits will occur every 4 weeks. From Weeks 28 until the Last Visit on Treatment visits will occur approximately every 12 weeks. Four to sixteen weeks after Last Visit on Treatment, patients will return for a final Follow-Up Visit. Study treatment will be terminated in all currently participating subjects when 250 narrowly defined MACE events have occurred in the study and all surviving patients have been followed for at least 24 weeks from randomization. At that time, all subjects will conduct their Last Visit on Treatment. Subjects will continue to take atorvastatin or rosuvastatin and will return 4 weeks after Last Visit on Treatment for the Follow-Up Visit. Procedures are defined in

Randomization		x											
Inclusion / Exclusion	x	x											
Medical History/Demographics	x												
ECG	x												
Vital Signs	x	x										x	
Physical Exam	x												
Central Laboratory:													
Fasting Lipid profile	x											x	
Hematology, HbA1c	x											x	
Chemistry	x											x	
Urinalysis	x											x	
Hepatitis Serology	x												
Liver Safety Panel	x	x	x	x	x	x	x	x	x	x	x	x	x
Biomarker Laboratory Tests													
Lipoproteins, fasting insulin		x										x	
Inflammation Panel		x						x					
Serum/Plasma Archive		x						x					
Pharmacogenomic		x			x								
MOCA		x											
EQ-5D-5L		x										x	
Adverse Events	x	x	x	x	x	x	x	x	x	x	x	x	x
Prior / Con. Medication	x	x	x	x	x	x	x	x	x	x	x	x	x
Drug Dispense/Account.	x	x	x	x	x	x	x	x	x	x	x	x	x

Table 1: Schedule of Events. The same visit schedule will apply to subjects who remain on assigned study treatment until the Last Visit on Treatment and to subjects who have prematurely discontinued study medication prior to the Last Visit on Treatment.

Liver safety:

- a) If ALT increase of >3 and ≤5xULN is confirmed on repeat measurement (within 3-4 days), subjects will be monitored every 3-4 days until the ALT is <1.5xULN.
- b) If ALT increase of >5xULN, investigational drug will be suspended. If confirmed on repeat measurement (within 3-4 days), investigational drug will be discontinued and subjects will be monitored every 3-4 days until ALT is <1.5xULN.

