	
covariance (ANCOVA) models with treatment group as a factor and the baseline value as a covariate.
 
No adjustment for multiplicity is needed for the primary hypothesis as there is no provision to terminate the trial for efficacy. A sequential gate-keeping approach will be used to control the overall Type I error rate when testing for the key secondary endpoints only if superiority is established for primary efficacy endpoint. The key secondary endpoints will be tested sequentially following a pre-specified order.
 
No multiplicity adjustment is planned to test the other secondary and exploratory endpoints.

--	---

Table 1: Schedule of Events

Study Visit	Screen	Treatment																		Follow Up (ET)	
	1	2	3	4	5	6	7	8	9	10	11	12	13	14	15	16	17	18	19 to end of study	LVT ¹	FU
Week	- 2 to -1	0	2	4	6	8	10	12	16	20	24	28	40	52	64	76	88	100	112, then every 12wks	end of study	LVT + 4wks ²
± No. Day			±3	±3	±3	±3	±3	±3	±3	±3	±3	±3	±7	±7	±7	±7	±7	±7	±7	±7	±7
Informed Consent	X																				
Randomization		X																			
Inclusion / Exclusion	X	X																			
Medical History/Demographics	X																				
ECG	X																				
Vital Signs	X	X									X			X		X		X		X	X
Physical Exam ³	X																	X		X	X
Central Laboratory:																					
Fasting Lipid profile ⁴	X										X			X		X		X		X	X
Hematology ⁵ , HbA1c	X										X			X		X		X		X	X
Chemistry ⁶	X										X			X		X		X		X	X
Urinalysis ⁷	X										X			X		X		X		X	X
Hepatitis Serology ⁸	X																				
Liver Safety Panel ⁹	X	X	X	X	X	X	X	X	X	X	X	X	X	X	X	X	X	X	X	X	X
Biomarker Laboratory Tests ¹⁰																					
Lipoproteins ¹¹ , fasting insulin		X									X			X		X		X		X	X
Inflammation Panel ¹²		X						X						X							
Serum/Plasma Archive ¹³		X						X						X							
Pharmacogenomic ¹⁴		X			X																
MOCA ¹⁵		X												X				X		X	
EQ-5D-5L		X									X			X		X		X		X	
Adverse Events	X	X	X	X	X	X	X	X	X	X	X	X	X	X	X	X	X	X	X	X	X
Prior / Con. Medication	X	X	X	X	X	X	X	X	X	X	X	X	X	X	X	X	X	X	X	X	X
Drug Dispense/Account.	X ¹⁶	X	X	X	X	X	X	X	X	X	X	X	X	X	X	X	X	X	X	X	X

¹Study treatment will be terminated in all currently participating subjects when the 250th event occurs and all surviving patients have been followed for at least 24 weeks from randomization. At that time all subjects actively treated will conduct their Last Visit on Treatment.

² 4 weeks after Last Visit on Treatment (LVT).

³ Physical Exam: height will be recorded only at Visit 1

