4.0 STUDY DESIGN

This is a double-blind, placebo-controlled, 2-arm parallel-group (allocation ratio 1:1), study of RVX000222 at a daily dose of 100 mg b.i.d. (total daily dose of 200 mg) or matching placebo in combination with high intensity statin therapy administered to T2DM subjects with history of recent CAD event and HDL-C level $<$ 40 mg/dL in males or $<$ 45 mg/dL in females.

After an initial screening period of 1 to 2 weeks during which subjects will demonstrate tolerance of high intensity statin therapy, subjects will be randomized to either RVX000222 100 mg b.i.d. or matching placebo with continued statin treatment. This combination treatment period will continue until 250 narrowly defined MACE events have occurred in the study and all surviving patients have been followed for at least 24 weeks from randomization. Blinded treatment with RVX000222 or matching placebo will then be discontinued. Subjects will remain on high intensity statin therapy for 4 more weeks until the Follow-Up Visit.

The study is an event-based trial and will continue until 250 primary endpoint events have occurred. Study treatment will be terminated after the 250th adjudicated event occurs. At that time, all subjects actively treated will conduct their Last Visit on Treatment and then be discontinued from investigational drug. Subjects will then return 4 weeks after last day of treatment for the Follow-Up Visit.

A Clinical Steering Committee (CSC) will oversee the conduct of the study. A Data Safety Monitoring Board (DSMB) will oversee the safety data for this study and independent CEC will adjudicate all suspected MACE composite events in an ongoing manner. An independent team (including an independent statistician) will perform the prospective unblinded analyses described in Section 10.8 (Data Safety Monitoring Board) and will report the results to the DSMB. Each committee will develop a charter to describe their activities and responsibilities prior to initiation of the study.

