6.10 Study Drug Interruption/Discontinuation

Treatment may be interrupted or discontinued at the discretion of the Investigator and Sponsor, based on AEs, other clinical laboratory data, vital signs measurements, and/or electrocardiogram (ECG) findings.

Subjects discontinuing study drug will continue participation in the study and will complete all remaining study visits. Discontinuation of assigned investigational drug (RVX000222 or placebo) or high intensity statin therapy should not result in study discontinuation. Subjects discontinuing investigational drug (RVX000222 or placebo) should be encouraged to continue on study-supplied high intensity statin therapy. For subjects who discontinue both investigational drug and study-supplied concomitant statin therapy, record alternative statin/lipid lowering therapy, if applicable.

	Screen	Treatment
--	---------------	------------------

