3.7. Study Visits

After randomization to RVX000222 or placebo, visits will occur every 2 weeks until Week 12. From Week 12 to Week 28, visits will occur every 4 weeks. From Week 28 until the Last Visit on Treatment, visits will occur approximately every 12 weeks. Four weeks after the Last Visit on Treatment, subjects will return for a final Follow-Up Visit. The Schedule of Events can be found in the study protocol. Study treatment will be terminated in all currently participating subjects when it is estimated that 250 subjects have experienced a narrowly defined MACE event. At that time, all subjects actively treated will conduct their Last Visit on Treatment as soon after as possible while ensuring at least 6 months of study therapy and then return 4 weeks after last day of treatment for the Follow-Up Visit. Procedures are defined in the Schedule of Events.

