8.4. Other Secondary and Exploratory Analysis

Other secondary and exploratory endpoints are listed in [sections 3.2.2.1](#) and [3.2.3](#). Quantitative endpoints that are defined as a (percent) change from baseline will be analyzed using analysis of covariance (ANCOVA) models with treatment group, baseline value, and strata as covariates. Descriptive statistics for (percent) change from baseline at each post-baseline visit will be summarized using the FAS.

Descriptive statistics (number of subjects with non-missing values, mean, standard deviation, minimum, 25th percentile, median, 75th percentile, and maximum) will be used to summarize continuous variables by treatment group for the FAS set.

Least squares (LS) means and difference in LS means between RVX000222 and Placebo with standard errors (SEs) and 2-sided 95% CI and p-values obtained from ANCOVA model will be presented at each applicable post baseline visit.

Mixed-effects model repeated measures analysis will be used to model percent change in measurements over time at the last visit on treatment (LVT). An unstructured covariance matrix will be used to fit the underlying MMRM model. Subject and error will be considered random effects; all effects that include treatment, strata and baseline value will be considered fixed.

The pattern of change from baseline over time will also be displayed graphically in Figures for some endpoints. No multiplicity adjustment is planned to test the other secondary and exploratory endpoints. Since most of the other secondary endpoints are clinical laboratory tests, they are also summarized under safety analysis in [section 9](#).

Analyses will summarize EQ-5D-5L scale and subscale scores at each visit and change from baseline at each visit.

Analyses will address mean differences by treatment group on MOCA scale and differences for subjects with a baseline score indicative of cognitive impairment (Baseline MoCA < 26)

9. Safety Analysis

Safety data such as clinical laboratory results, vital signs, findings from physical examinations will be listed and/or summarized by treatment group where appropriate. No inferential hypothesis testing will be performed on the safety variables.

The assessment of safety will be based on the frequency, intensity, and types of AEs and for change and from Baseline in the clinical laboratory variables, and vital sign measurements.

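### The Last Visit on Treatment is limited to actively treated subjects in five places, against the trial's own rule that subjects who stop drug complete every remaining visit

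*Protocol*

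**What the plan says.** **Narrow wording.** Protocol Table 1, footnote 1: "At that time all subjects actively treated will conduct their Last Visit on Treatment". SAP 4.5 and footnote 1 of the SAP schedule repeat this. Protocol 4.0: "At that time, all subjects actively treated will conduct their Last Visit on Treatment and then be discontinued from investigational drug". SAP 3.7: "At that time, all subjects actively treated will conduct their Last Visit on Treatment as soon after as possible".

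**Broad wording.** Synopsis, Study Procedures: "At that time, all subjects will conduct their Last Visit on Treatment". The Table 1 legend in the synopsis extends the same visit schedule "to subjects who have prematurely discontinued study medication prior to the Last Visit on Treatment". Protocol 6.10, repeated in SAP 3.4: "Subjects discontinuing study drug will continue participation in the study and will complete all remaining study visits".

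**Follow-Up Visit.** Table 1 footnote 2, Protocol 7.2.17 and SAP 4.5 place it 4 weeks after the Last Visit on Treatment (LVT). Protocol 4.0 counts 4 weeks from the last day of treatment, and so does SAP 3.7: "and then return 4 weeks after last day of treatment for the Follow-Up Visit". The synopsis gives a range of four to sixteen weeks after the LVT and then, in the same paragraph, 4 weeks.

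**Use in the analysis.** SAP 8.4 says the repeated-measures model "will be used to model percent change in measurements over time at the last visit on treatment (LVT". SAP 4.4.1 analyses the FAS by randomized group. Protocol 9.8 and SAP 4.5 rule out imputing results.

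**The concern.** The LVT is the close-out collection point for lipids, HbA1c, chemistry, apolipoproteins and fasting insulin (the last two in the biomarker subset), EQ-5D-5L and MOCA (Protocol 7.2.16). If sites hold it only for subjects still on drug, the values at that visit describe those who tolerated treatment, while the SAP presents a comparison by randomized group.

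The selection could differ by arm. Protocol 1.0 names transaminase elevation as the dose-limiting toxicity, with ALT above 3xULN in 7-8% of subjects, and Protocol 6.10.1 discontinues drug on confirmed ALT above 5xULN.

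For time-to-event endpoints, subjects without an event are censored at last contact (SAP 8 and 8.2). A skipped visit therefore removes one scheduled contact near study end and can bring the censoring date forward.

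**Working it through.** This is mainly a comparison of texts. The arithmetic only shows how little the primary design depends on it.

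**1. Who has the LVT?**

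| Place | Subjects assigned the visit |
|---|---|
| Protocol Table 1, footnote 1 | actively treated |
| Protocol 4.0 | actively treated |
| SAP 3.7 | actively treated |
| SAP 4.5 | actively treated |
| SAP schedule, footnote 1 | actively treated |
| Synopsis, Study Procedures | all subjects |
| Synopsis, Table 1 legend | same schedule on or off drug |
| Protocol 6.10 and SAP 3.4 | all remaining visits after stopping drug |

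The first five rows conflict with the last three. Table 1 itself carries both rules, one in its footnote and one in its legend. The remaining-visits rule does not settle the matter, because the footnote decides whether the LVT is a remaining visit for someone off drug.

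**2. What is collected only there?** Visit 19 and later visits collect only the liver safety panel (Protocol 7.2.15), so after Week 100 the LVT is the next occasion for the other laboratory tests and both questionnaires. The Follow-Up Visit repeats the laboratory tests but neither EQ-5D-5L nor MOCA (Protocol 7.2.17). An off-drug subject with no LVT therefore has no close-out value for either instrument, and laboratory values only at the later visit.

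**3. What does the SAP do with it?** Section 8.4 targets the LVT in the mixed model, summarizes EQ-5D-5L at each visit and compares MOCA means by arm. It does not say whether an off-drug subject has an LVT value. The visit-window table in SAP 4.5 ends at Week 112 with no LVT row.

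**4. Do the two Follow-Up anchors agree?** For a subject on drug until closure, treatment ends at the LVT and they essentially coincide. For one who stopped earlier they do not.

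**5. Primary design figure.** Inputs from Protocol 9.2: 250 events, hazard ratio 0.7, two-sided 5%; allocation is 1:1. Power = Φ(√(250/4) × |ln 0.7| − 1.96) = Φ(7.906 × 0.3567 − 1.96) = Φ(0.860) = 80.5%. This reproduces the stated 80% or so, and neither wording changes it.

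**6. A deliberately harsh bound, not an estimate.** The documents give no drug-stop rate. Assume that a share q of 2400 subjects is off drug, that 88% of them are event-free, and that every event in a closing gap of w weeks is lost.

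- Placebo hazard = −ln(1 − 0.105)/1.5 = 0.0740 per year; average of the two arms = 0.85 × 0.0740 = 0.0629.
- Events lost = 2400 × q × 0.88 × 0.0629 × w/52.18. Power is then recomputed with 250 minus that number.

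| q | w (weeks) | Events lost | Power |
|---|---|---|---|
| 5% | 6 | 0.8 | 80.4% |
| 10% | 12 | 3.1 | 80.0% |
| 30% | 16 | 12.2 | 78.5% |

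The longest gap is one 12-week visit interval plus the 4 weeks to Follow-Up. Subtracting from 250 is harsh, because Protocol 4.0 runs the trial until 250 events have occurred.

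**The case against.** The strongest reply is that the intended design is clear and only the wording slipped. The Table 1 legend, Protocol 6.10 and SAP 3.4 keep early stoppers on the schedule. Protocol 6.10.3 offers subjects who ask to withdraw continued visits without drug, or telephone contact with the LVT and Follow-Up Visit in clinic if possible. It asks for efforts to perform the procedures of both visits even when no further contact is wanted. SAP 8.2 follows everyone to drop-out, death or study closure, and describes drop-out as withdrawn consent or loss to follow-up, not stopping drug. Potential MACE are reported as SAEs (Protocol 8.2.3.5), within 24 hours of the investigator's awareness (8.2.3.3).

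Most of this stands, and it rules out three stronger readings that a reader might infer:

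- *Late primary events are missed.* The documents do not support this. Follow-up to closure and SAE reporting do not depend on the LVT. What could be lost is one scheduled contact.
- *A subject who stops early can be discharged four weeks later.* The sentence in SAP 3.7 starts at study closure and concerns subjects still treated then. It does not govern someone who stopped earlier.
- *Biomarker effects at the LVT are inflated in proportion to the share off drug.* That needs a drug-stop rate that the documents do not give and an effect that vanishes off drug. It also ignores that the mixed model uses off-drug values from earlier visits.

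The reply does not remove the contradiction. The restriction stands in five places, including both schedule footnotes, and no text says which rule governs.

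**Conclusion.** The plan is wrong as written on this point, with modest consequences. The assignment of the LVT contradicts the trial's full-follow-up rule. Read literally, it leaves off-drug subjects without the values that SAP 8.4 uses at that visit. The firmest harm is to the other secondary and exploratory endpoints: it is unclear whose values the LVT analysis includes, and any missingness could be related to arm.

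The documents do not show that sites will follow the narrow wording, nor how many subjects will stop drug, so the size cannot be quantified from them. The effect on the primary analysis is likely small: power is 80.5% under either wording, and even the harsh assumptions above leave it at 78.5% or more.

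**What to change.** 1. In Protocol Table 1 footnote 1, Protocol 4.0, SAP 3.7, SAP 4.5 and the SAP schedule footnote, replace the restriction to actively treated subjects with *all subjects still in the study, on or off investigational drug*.
2. Time the Follow-Up Visit from that visit throughout. This means reconciling the last-day-of-treatment anchor in Protocol 4.0 and SAP 3.7, and the four-to-sixteen-week range in the synopsis.
3. State in SAP 8.4 that off-drug subjects' end-of-study values enter the FAS analysis at the LVT.

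The cost is wording, plus visits and samples from off-drug subjects at sites that would otherwise have skipped them. The synopsis and Protocol 6.10 already imply those visits. Questionnaire values not collected at close-out cannot be recovered later.

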1.0 BACKGROUND AND STUDY RATIONALE

The majority (75%) of deaths in subjects with diabetes mellitus (DM) are due to atherosclerotic cardiovascular disease (CVD). In the United Kingdom Prospective Diabetes Study, after 9 years of follow-up, fatal CVD events were 70 times more frequent than fatal microvascular complications. High residual risk of CVD events remains, even in subjects with controlled low-density lipoprotein cholesterol (LDL-C). Recent studies suggest a major adverse cardiovascular event (MACE) rate of >11% over 18 months in type 2 diabetes mellitus (T2DM) despite a baseline LDL-C of <2.1 mmol/L. There is, therefore, an urgent need for new approaches to reduce MACE in subjects with CVD, especially for T2DM subjects.

Bromodomains (BRDs) are a family of evolutionary conserved protein-interaction modules that play key functions in chromatin organization and regulation of gene transcription. One recognized family of bromodomain-containing proteins is the bromodomain and extra-terminal (BET) family. BET inhibition represents a novel, epigenetic approach to treat CVD. RVX000222 is the first oral agent in the BET inhibitor class that preferentially targets BET protein 4 (BRD4) thereby regulating gene activity. RVX000222 affects biological processes important in atherosclerosis and acute coronary events via selective inhibition of BET proteins. RVX000222 selectively binding to the bromodomains (BD1/2) of the BET proteins with a 20-fold higher affinity to the second domain (BD2) versus the first (BD1). This feature of RVX000222 differentiates it from all other known BET inhibitors that have equal affinity of binding to either BD1/2. RVX000222 affects a single target (the second domain [BD2] of the bromodomain system) with multiple biological actions. The discovery of RVX000222 in 2006 stemmed from the screening of chemical compounds that had the ability to increase apolipoprotein A-I (ApoA-I) gene expression when exposed to human hepatoma cells. Initial cellular assays involving treatment with RVX000222 led to a rapid but direct effect in reducing IL-6 and VCAM-1 mRNA by 4 hours. In contrast, induction of ApoA-I mRNA and protein production required 24-48 hours suggesting an indirect effect. During the course of RVX000222 development, studies into the mechanism of action further demonstrated that its activity on atherosclerosis extended beyond its effects on ApoA-I/HDL. We now know that the lipid modifying effects are likely a minor contributor to efficacy of the compound. Indeed, current studies of RVX000222 show that it has effects on vascular inflammation, the complement and coagulation cascades, and acute phase response pathways all of which have known roles in cardiovascular disease and acute cardiac events. Gene expression regulation by BET proteins appears to be at the root of the pathogenesis of cardiac events. The effect of selective BET inhibition on all of the pathways outlined above underlies the potential benefit of using RVX000222 in treating CVD risk and for the prevention of recurrent acute events.

RVX000222 is available as a capsule formulation with standard excipients and established stability.

A total of 985 subjects have participated in completed trials, of which 706 received treatment with RVX000222 including 130 healthy volunteers and 576 subjects with stable coronary artery disease (CAD) and/or dyslipidemia on standard of care therapy. Three Phase 2 studies in subjects with CVD have been completed: a 12-week study (RVX222-CS-005; ASSERT) in which 299 subjects with stable CAD on standard of care therapy were enrolled, coupled with 24-week (RVX222-CS-008; SUSTAIN) and 26-week (RVX222-CS-007; ASSURE) studies in statin treated subjects with stable CAD and/or dyslipidemia, with low baseline HDL-C concentrations. The latter two studies enrolled 176 and 323 subjects, respectively. An additional Phase 2 study in subject with pre-diabetes (RVX222-CS-010) that enrolled 20 subjects was also completed.

The metabolism and disposition of RVX000222 after oral administration in humans, is similar to what occurs in animals. The parent molecule is metabolized to the same two inactive primary metabolites (RVX000288 [carboxylic acid] and RVX000404 [glucuronide]), with only about one-tenth of the dose excreted in the urine as a combination of parent and metabolite. It appears to be reasonably well absorbed, and exhibited dose-proportional increases in exposure (area under time curve [AUC]) between 1 and 4 mg/kg. The terminal half-life of the drug is about 11 hours. An increase in bioavailability of approximately 60% when given with food led to a recommendation that dosing with meals is required for further clinical studies. On a b.i.d. treatment schedule, steady-state kinetics were achieved within about 1

day of treatment. RVX000222 is expected to have low risk for producing drug-drug interactions, based on available data related to inhibition or induction of cytochrome P450 enzymes.

Positive changes in CVD biomarkers were seen in both normal volunteer and subject studies and led to the identification of a total daily dose of 200 mg (100 mg b.i.d taken with meals) as the optimum balance of efficacy and adverse events (AEs). The changes in biomarkers observed in the longer term Phase 2 studies are shown in Table 2.

Table 2: Effects of RVX000222 on Biomarkers of CV Risk – Lipids and Inflammation (ASSURE and SUSTAIN Trials)

Biomarker	Placebo (n=166)		RVX000222 (n=331)		p value vs. placebo
	Percent Change	p value vs. baseline	Percent Change	p value vs. baseline	
HDL Cholesterol, (mg/dL)	0	0.59	7.69	<0.0001	0.0003
ApoA-I, (mg/dL)	3.8	0.0003	10.3	<0.0001	0.005
Total HDL particles, (μmol/L)	0.4	0.61	6.51	<0.0001	0.07
HDL particle size, (nm)	0	0.3	1.16	<0.0001	0.049
Large HDL particles, (μmol/L)	4.11	0.02	30.71	<0.0001	0.03
hs-CRP, (mg/L)	-22.4	0.0002	-28.4	<0.0001	0.67
ALP, (U/L)	-3.23	0.03	-11	<0.0001	<0.001

Results expressed as median percentage change from baseline. Source: RVX000222 data on file. Modified intention to treat population, 2-sided van Elteren test of RVX000222 vs. placebo, stratified by trial. Wilcoxon signed-rank test for within group comparison vs. baseline.

The data from all three individual Phase 2 studies in CVD patients showed independent, consistent trends for fewer MACE in RVX000222-treated subjects versus subjects receiving placebo. In the ASSERT study, 2.2% of subjects treated with RVX000222 experienced a MACE compared to 2.7% of placebo-treated subjects during 12 weeks of therapy. In the SUSTAIN study, MACE occurred in 7.5% of placebo-treated subjects and only 0.4% of RVX000222-treated subjects ($p < 0.06$) after 24 weeks of therapy. This trend was also observed in the ASSURE trial, with 14.3% of placebo-treated subjects experiencing MACE compared to 7.5% of subjects in the RVX000222-treated group after 26 weeks of therapy, an approximately 48% difference ($p < 0.1$).

Given the promising findings of reduced MACE from these three studies, a post-hoc meta-analysis was conducted using the pooled data ($n = 798$). Collectively, there was a statistically significant ($p = 0.023$) reduction in MACE as defined by death, myocardial infarction (MI), coronary revascularization, or cardiovascular hospitalization (CV) as shown in Figure 1. Subjects receiving RVX000222 were 44% less likely to experience a MACE compared to placebo with only 5.9% of RVX000222-treated subjects experiencing any MACE compared to 10.4% for placebo-treated subjects. Approximately 80% of subjects were treated with high intensity statin therapy (atorvastatin and rosuvastatin).

[figure not shown]

Figure 1: MACE in Subjects Treated in RVX000222 Phase 2 Studies

Overall, RVX000222 was generally well tolerated and AEs were mild with little discernible difference between placebo- and the RVX000222-treated subjects. The dose-limiting toxicity for RVX000222 is a generally non-symptomatic elevation in serum transaminases (alanine aminotransferase [ALT] and in some cases aspartate aminotransferase [AST]), without adversely affecting total bilirubin values in any subject. There was no increase in alkaline phosphatase (ALP) observed. There was an overall incidence of 7-8% of subjects with ALT >3x the upper limit of normal range (ULN). There was often confounding with use of drugs known to increase ALT (diclofenac and clavulanic acid) or prior history of hepatitis. Raised enzymes return promptly to within the normal transaminase range (approximately 15 days for ALT >5xULN), suggesting that any hepatocellular effect can be reversed by suspending treatment with investigational drug. For subjects with elevations >3xULN and <5xULN, treatment was continued and all returned to normal levels. Subjects with ALT elevations >5x and <8xULN were dose interrupted, re-challenged at a lower dose and the majority successfully completed the studies. Drug-induced ALT elevations >3xULN were observed between weeks 4-12 across all 4 completed Phase 2 trials, with one exception. One subject with elevated ALT and AST at Week 20 due to cholecystitis was noted in RVX222-CS-007. No cases of Hy's Law have been detected.

A possible mechanism implicated in the elevation of serum transaminases is the effect of BET inhibition on hepatic bile acids through changes in expression of the farnesoid X receptor (FXR) and cholesterol 7-alpha hydroxylase (CYP7A1). Hepatocyte cell culture studies show that RVX000222 represses FXR expression. Increased expression of CYP7A1, a rate limiting enzyme in bile acid synthesis, is observed in select donors of primary hepatocytes as a consequence of FXR repression. Increased CYP7A1 expression predicts increased bile acid synthesis. Intracellular concentrations of bile acids may be further augmented through downregulation of BSEP, a bile acid export pump. Increased bile acid synthesis, combined with a decrease in BSEP-mediated biliary excretion of bile acids, may mediate ALT elevations in select patients where CYP7A1 is induced. In healthy volunteers or CVD patients taking RVX000222, serum bile acids appear to track with ALTs. Elevation of serum bile acids preceded serum ALT elevation, suggesting that the bile acid-mediated mechanism is plausible. However, other markers of liver damage such as bilirubin or LDH are not elevated and serum bile acids although increased from baseline remain in a normal range.

Minimizing residual risk of MACE in T2DM subjects' post-acute coronary syndrome (ACS) addresses an important unmet medical need. RVX000222 and BET inhibition represent a potential new treatment mechanism for subjects at high risk for CVD. Based on the data above, the BETonMACE study (RVX222-CS-015) will focus on prevention of subsequent MACE in subjects with CAD and DM with high intensity statin therapy as co-medication.

